6.1.11. Visit Schedule

The schedule of visits including which study related procedures are to be performed and which samples are to be collected at each time point is described graphically in Appendix 1A (A Cohorts), 1B (B Cohorts), and 1C (C Cohorts).

6.1.12. Visit Days and Numbering

Mandatory visits include the Screening visit, C1D1, C1D8, and Day 1 (± 3 days) of subsequent cycles, and the End of Treatment (EOT) visit. Patients may be required to make visits for PK samplings. Other visits may occur as required for standard of care medical practice.

If a patient comes early to begin a new cycle (for example, coming on Cycle 3 Day 28 would be equivalent to Cycle 4 Day -1), all study related procedures including, physical exam, clinical safety laboratory, CT scans if applicable, and study drug dispensing can occur, but Day 1 of the next cycle is not renumbered.

If a patient comes late to begin a new cycle but has missed doses of study medication, the day that the study medication is resumed shall be designated Day 1 of the next cycle (i.e., the previous cycle is lengthened).

If a patient's temporary discontinuation of study medication overlaps Day 1 of a subsequent cycle, the day that the study medication is resumed shall be designated Day 1 of the next cycle (i.e., the previous cycle is lengthened). If a patient holds study drug mid-cycle but resumes before Day 1 of a subsequent cycle, the cycle days are not renumbered.

Other alterations to the visit schedule, cycle numbering, or the \pm 3 day window must be discussed with the medical monitor and recorded as a protocol deviation.

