6.1.7. Dose Modifications and Dose Delay

Investigators should follow the guidelines described herein for the modification of MS-553 treatment. Any plan to deviate from these guidelines in view of patient safety must be

previously discussed with the study Sponsor and the medical monitor unless there is an urgent need for action.

All dose modifications should be based on the worst preceding toxicity. If study treatment is being held due to toxicity, scheduled visits and all safety assessments in Cycle 1 should continue to occur, even without dispensation of the study drug. Additional scheduled visits and assessments including all PK samplings may be adjusted according to the actual dosing schedule upon the agreement between the investigator, the study medical monitor, and the Sponsor.

Recommended modifications to dosing (not including dose-limiting toxicities in the first cycle) are described in Appendix 2A (MS-553 Recommended Dose Modifications and Delays for Toxicity).

A maximum of three dose reduction steps but not lower than 100 mg BID as a single agent will be allowed, after which the patient will be discontinued from study treatment if there is a need for further dose reduction. In the combination regimens of cohort B and C, dose reductions to not lower than 50 mg BID is allowed.

For patients who undergo dose interruptions (delays) due to toxicity, if the same toxicity returns after re-initiation of treatment, regardless of duration, the second re-initiation of study drug must resume at the next lower dose level. However, the dose of MS-553 that is restarted could be reduced if the investigator feels it prudent to re-challenge at a lower dose. Please refer to Appendix 2A for dose modification instructions.

Recommended modifications to dose and schedule for the combination treatments are outlined in Appendix 2B and 2C, and according to institutional standard of care.

If the patient requires a dose interruption of > 28 days from previous dose for either MS-553 or combination treatment, then the patient must be discontinued from study treatment. Patients who discontinue the treatment due to an adverse event or an abnormal laboratory value, even if not related to study drug, must be followed until resolution or stabilization of the event.

All dose changes or interruptions must be recorded in the dosage administration record CRF.

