6.2.2. Efficacy

Response assessments will be made by the individual investigators. Response for CLL will be evaluated according to criteria published by 2008 IWCLL. Because of the well-documented lymphocytosis not associated with disease progression that occurs with BCR signaling inhibitors such as BTK inhibitors, progressive lymphocytosis in the absence of other signs of disease progression (e.g., splenomegaly, enlarging lymph nodes, and disease-related constitutional symptoms) will not be considered disease progression. Isolated lymphocytosis in the context of what would otherwise be a PR is defined as a PR with lymphocytosis (noted as PR-L, PR+L, or PRwL in literature). Response criteria in the SLL patients and aggressive lymphoma patients will be based on the International Working Group consensus response evaluation criteria in lymphoma (RECIL 2017).

Initial evaluation of the efficacy endpoints related to response will incorporate the data from the first 9 cycles of treatment. Any patient who receives at least one dose of study therapy is evaluable for response. Patients who have stable disease or a response by 9 cycles and continue treatment after 9 cycles will have response assessments including CT scans of the chest, abdomen, and pelvis (and neck if involved), preferably least every 12 weeks, or as clinically indicated until disease progression. Patients who do not have a response by 9 cycles but who have stable disease are eligible to stay on study treatment for up to a total of 24 cycles, with continue to have stable disease after 24 cycles or have a response after 9 cycles therapy, drug therapy can continue until disease progression.

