- b. S/RFU (Safety/Response Follow Up); Patients who discontinue treatment for progressive disease and/or use of other CLL/SLL therapy will be followed for survival every 24 weeks (± 7 days) for up to 3 years. Patients who discontinue treatment for reasons other than progressive disease, use of other CLL/SLL therapy, death, or withdrawal of consent will have response assessments every 12 weeks (± 7 days) until progressive disease occurs. Thereafter they will be followed for survival every 24 weeks (± 7 days) for up to 3 years. All patients will discontinue survival follow-up upon completion of 3 years of survival follow-up, withdrawal of consent, death, or study closure, whichever is the earliest. For assessment of survival, only a review of patient chart and/or a phone call is required.
- c. 100, 200, 250, 300 mg or intermediate doses PO BID according to dose level. Study staff should record clinic-administered doses in the dosing diary and patient should record home doses in the dosing diary.
- e. Serum chemistry should include albumin, alkaline phosphatase, AST, ALT, bicarbonate, BUN, calcium, creatinine, glucose, LDH, magnesium, phosphate, potassium, sodium, total bilirubin, total protein, and uric acid.
- f. A urine pregnancy test should be performed with screening in every woman of childbearing potential prior to study entry.
- g. In the CLL/SLL cohorts, CT scans of the chest, abdomen, and pelvis (and neck if involved) should occur at screening and at the post 3, post 6, and post 9 cycles of therapy assessments (i.e., at or prior to Cycle 4 Day 1, Cycle 7 Day 1, and Cycle 10 Day 1). Patients who continue with drug therapy after 9 cycles

of treatment should have CT scans, preferably every 12 weeks, or as clinically indicated until disease progression. In the aggressive lymphoma cohort, CT scans of the chest, abdomen, and pelvis (and neck if involved) should occur at screening and as clinically indicated or at a minimum of every 24 weeks while on treatment. Other image tools for response assessment may be used per RECIL 2017 for lymphomas.

- h. Screening procedures shall be performed within 28 days prior to first dose of study drug. Studies performed at the study site prior to patient signing of informed consent can be utilized for screening purposes if obtained within 28 days before first dose of study drug, except in the case of *IGHV* mutation status which are permitted to have been obtained at any time prior to screening.

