- b. S/RFU (Safety/Response Follow Up); Patients who discontinue treatment for progressive disease and/or use of other CLL/SLL therapy will be followed for survival every 24 weeks (± 7 days) for up to 3 years. Patients who discontinue treatment for reasons other than progressive disease, use of other CLL/SLL therapy, death, or withdrawal of consent will have response assessments every 12 weeks (± 7 days) until progressive disease occurs. Thereafter they will be followed for survival every 24 weeks (± 7 days) for up to 3 years. All patients will discontinue survival follow-up upon completion of 3 years of survival follow-up, withdrawal of consent, death, or study closure, whichever is the earliest. For assessment of survival, only a review of patient chart and/or a phone call is required.
- c. 100, 200, 250, or 300 mg PO BID according to dose level. Study staff should record clinic-administered doses in the dosing diary and patient should record home doses in the dosing diary.

- e. Serum chemistry should include albumin, alkaline phosphatase, AST, ALT, bicarbonate, BUN, calcium, creatinine, glucose, LDH, magnesium, phosphate, potassium, sodium, total bilirubin, total protein, and uric acid.
- f. A urine pregnancy test should be performed with screening in every woman of childbearing potential prior to study entry.
- g. In the CLL/SLL cohorts, CT scans of the chest, abdomen, and pelvis (and neck if involved) should occur at screening and at the post 2, post 6, and post 9 cycles of therapy assessments (i.e., at or prior to Cycle 3 Day 1, Cycle 7 Day 1, and Cycle 10 Day 1). Patients who continue with drug therapy after 9 cycles of treatment should have CT scans, preferably every 12 weeks, or as clinically indicated until disease progression. In the aggressive lymphoma cohort, CT scans of the chest, abdomen, and pelvis (and neck if involved) should occur at screening and as clinically indicated or at a minimum of every 24 weeks while on treatment.
- h. Screening procedures shall be performed within 28 days prior to first dose of study drug. Studies performed at the study site prior to patient signing of informed consent can be utilized for screening purposes if obtained within 28 days before first dose of study drug, except in the case of *IGHV* mutation status which are permitted to have been obtained at any time prior to screening.

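### In the CLL/SLL cohorts, the CT due dates of the first nine cycles move with dose holds, so scan timing depends on tolerability, with a small average effect on PFS and stable disease

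*Combined protocol and SAP*

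**What the plan says.** Section 6.1.12 gives the cycle-numbering rule. For a hold that runs over a scheduled Day 1, the rule is that "the day that the study medication is resumed shall be designated Day 1 of the next cycle (i.e., the previous cycle is lengthened"). The same applies when a patient comes late for a new cycle and has missed doses. A shorter hold has no such effect: "If a patient holds study drug mid-cycle but resumes before Day 1 of a subsequent cycle, the cycle days are not renumbered".

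Section 6.1.7 caps a single interruption. "If the patient requires a dose interruption of > 28 days from previous dose" of MS-553 or the combination treatment, study treatment stops. It also allows scheduled assessments outside the Cycle 1 safety assessments to follow actual dosing, by agreement.

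Footnote g of Appendices 1A and 1B places the early CLL/SLL scans "at the post 3, post 6, and post 9 cycles of therapy assessments (i.e., at or prior to Cycle 4 Day 1", with the later two by C7D1 and C10D1. Appendix 1C has "at the post 2, post 6, and post 9 cycles of therapy assessments (i.e., at or prior to Cycle 3 Day 1", then C7D1 and C10D1. After nine cycles, footnote g moves to scans preferably every 12 weeks or as clinically indicated. Patients who stop treatment without progression are assessed every 12 weeks ± 7 days (Section 3.2).

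On the endpoint side, Section 6.2.2 states: "Initial evaluation of the efficacy endpoints related to response will incorporate the data from the first 9 cycles of treatment". Sections 2.5 and 6.2.2 measure PFS from first dose, and define stable disease as lasting at least 6 months from the start of MS-553 monotherapy to documented progression.

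**The concern.** The scan clock counts cycles and the endpoint clock counts days. They agree in a patient who never misses a Day 1 and separate in one whose hold runs over it. How often a patient is imaged in the first nine cycles then depends on tolerability, which is itself an outcome of treatment.

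Three results are exposed. PFS dated by CT can lengthen with the scan interval. The 6-month stable-disease rule, which feeds the disease control rate, can be met because a scan was late. The nine-cycle response evaluation also covers more calendar time in patients with holds.

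Nothing else in the plan anchors the dates. The other response data are collected on Day 1 of each cycle (Section 3.7), so they move too. Section 6.2.2 refers to Section 8 for censoring, but Section 8 has no censoring rule and no rule for late or missed scans. Cohort A2 puts 20 patients on each of DS1 and DS2 before a final RP2D, so any difference in hold rates would carry over into a descriptive reading of their PFS.

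**Working it through.** The plan states no figure for this effect, so there is none to reproduce.

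**Inputs from the protocol.** 28-day cycles; scans after 3, 6 and 9 cycles (Cohort C: 2, 6 and 9); an interruption cap of 28 days from the previous dose.

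**Scan dates.** Study day = 28 × completed cycles + 1 + total shift of Day 1.
- No hold, A1, A2 and B: 28×3+1 = 85, 28×6+1 = 169, 28×9+1 = 253 (weeks 12, 24, 36).
- No hold, C: days 57, 169, 253 (weeks 8, 24, 36).
- One shift of 7, 14 or 28 days stretches an 84-day interval to 91, 98 or 112 days, or 13, 14 or 16 weeks (+8%, +17%, +33%).
- One 28-day shift in each three-cycle block gives weeks 16, 32 and 48.

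The cap counts from the previous dose, so only a hold that starts at the cycle boundary gives close to the full 28 days.

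**Effect on the progression date.** Assumptions: exponential progression times with medians of 6, 9, 12 or 18 months (month = 30.4375 days), progression dated at the next scan, one shift of *h* days before the first CT, and 84-day intervals afterwards. A progression is dated *h* days later, unless it falls within *h* days after a nominal scan. In that case the shifted scan finds it 84 − *h* days sooner. If *p* is the share of progressions in the second group, then

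mean added delay = *h*(1 − *p*) − (84 − *h*)*p* = *h* − 84*p*.

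For *h* = 14:

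| Assumed median | *p*, all progressions | Added delay, all | *p*, first 252 days | Added delay, first 252 days |
|---|---|---|---|---|
| 6 months | 0.138 | 2.4 days | 0.106 | 5.1 days |
| 9 months | 0.147 | 1.7 days | 0.108 | 4.9 days |
| 12 months | 0.152 | 1.3 days | 0.109 | 4.8 days |
| 18 months | 0.157 | 0.9 days | 0.110 | 4.8 days |

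Simulation with 1,000,000 draws per median agrees: in the first 252 days the mean lag from progression to its dating rises from 43–44 days with no hold to 47–49 days. For one 28-day shift it rises to 52–55 days, an increase of about 10–11 days; over all progressions the increase is about 2–5.5 days.

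**Individual patients.** Progression on day 80 after first dose is dated day 84 on the nominal schedule and day 98 after a 14-day shift. Progression on day 90 is dated day 168 on the nominal schedule and day 98 after the same shift. About 14–16% of progressions are dated earlier (the *p* column for all progressions).

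**Cohort level.** The documents give no hold rate. If 10% to 40% of patients had one 14-day shift, the mean delay would be 0.10×5 = 0.5 to 0.40×5 = 2.0 days for early progressions. Over all progressions it would be 0.10×0.9 ≈ 0.1 to 0.40×2.4 ≈ 1.0 day.

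**Stable-disease threshold.** C7D1 is 28×6 = 168 days after first dose. Six calendar months are 6×30.4375 ≈ 183 days. Progression first seen at an unshifted C7D1 fails the threshold. With a shift of 183 − 168 = 15 days or more, the same disease course meets it. This needs 6 months to mean calendar months; if it meant six 28-day cycles (168 days), the unshifted scan would already meet it.

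**The case against.** The case for leaving the schedule alone has weight. Scans are due at or before each Day 1, so a week 12 scan during a hold complies: lateness is allowed, not required. Mid-cycle holds do not renumber. After cycle 9, and after stopping treatment without progression, the schedule is already in calendar weeks. Assessing response after equal numbers of treatment cycles is a coherent choice for a descriptive response rate. Twelve-weekly scanning already carries a mean lag of about 43 days, so a few more days matter little. All of this stands. It limits the size of the point but does not remove the link between holds and scan dates.

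A reader might infer more than the documents support:
- That every affected progression is dated later by the full shift, so that 14-day shifts in 10% to 40% of patients cost 1.4 to 5.6 days (0.10×14 to 0.40×14). This ignores progressions that the shifted scan finds sooner.
- That all cohorts are affected. Footnote g schedules the aggressive lymphoma cohort (A3, to be closed) as clinically indicated or at least every 24 weeks, not by cycle.
- That OS is affected. It runs to death and does not depend on scans.
- That DoR is lengthened. Response onset can also be detected later, so the direction is uncertain.
- That the less tolerated of DS1 and DS2 will look better on PFS. No hold rates are given, no passage makes PFS or DoR a criterion for the final RP2D, and Sections 8.2 and 8.4 disclaim power and formal hypotheses.

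**Conclusion.** The point holds for the three on-treatment CTs of the first nine cycles in the CLL/SLL cohorts. Their latest due dates can slip by up to about 4 weeks per hold that overlaps a Day 1, and only in patients with interruptions. The result is later dating of CT-detected progression on average, not in every patient, and an occasional change of stable-disease status at C7D1. The size rests on assumed medians, an exponential form, and scans taken at the latest due date. The cohort effect is probably a few days at most, on descriptive endpoints only. This is a cheap improvement in wording, not a flaw that threatens the trial's conclusions.

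**What to change.** - **Footnote g, Appendices 1A and 1B:** set the CLL/SLL scans at weeks 12, 24 and 36 from C1D1 (± 7 days), regardless of holds or cycle renumbering.
- **Footnote g, Appendix 1C:** keep the pre-venetoclax scan tied to C3D1, and set the later two at weeks 24 and 36 (± 7 days).
- **Scans after cycle 9:** keep the existing wording.
- **Section 6.1.12:** add that cycle renumbering does not move response imaging.
- **Section 6.2.2:** define the initial response evaluation as data through the week 36 scan.

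The scans then fall on nominal days 85, 169 and 253 whatever the holds, and the hold-dependent shift is zero. The latest week 24 scan is 168 + 7 = 175 days after first dose, still short of 183, so the window itself cannot carry a progression over the stable-disease threshold. The number of early scans and the dosing rules do not change. The cost is that a scan may fall away from a dosing visit in a patient on hold.

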6.2. Assessments of Safety, Efficacy, and Exploratory Endpoints

6.2.1. Safety

For Cohort A1, assessments for DLT and TEAE will occur during Cycle 1. For Cohort B1 and C1, assessments for DLT and TEAE will occur during defined DLT evaluation periods (see Sections 0 and 3.3.4). TEAE will be assessed during the course of the trial. The primary endpoint will be the rate of DLT and TEAE requiring study drug discontinuation in the DLT evaluable period.

Toxicities will be defined using NCI CTCAE v5.0 criteria in Appendix 4.

Safety assessments will consist of monitoring and recording all adverse events, including serious adverse events, the monitoring of hematology, blood chemistry, and the regular monitoring of vital signs, ECGs, and physical condition as shown in Appendix 1A (A Cohorts), 1B (B Cohorts), or 1C (C Cohorts). For details on AE collection and reporting, refer to Section 7, Adverse Events and Toxicity Management. If a patient has vision-related adverse event that is \geq Grade 2 and deemed at least possibly related to the drug, the patient will be referred to an ophthalmologist for a typical 8-point exam including measurement of visual acuity, slit-lamp bio-microscopy, and dilated full-fundus examination of the macula, optic nerve and peripheral retina.

6.2.2. Efficacy

Response assessments will be made by the individual investigators. Response for CLL will be evaluated according to criteria published by 2008 IWCLL. Because of the well-documented lymphocytosis not associated with disease progression that occurs with BCR signaling inhibitors such as BTK inhibitors, progressive lymphocytosis in the absence of other signs of disease progression (e.g., splenomegaly, enlarging lymph nodes, and disease-related constitutional symptoms) will not be considered disease progression. Isolated lymphocytosis in the context of what would otherwise be a PR is defined as a PR with lymphocytosis (noted as PR-L, PR+L, or PRwL in literature). Response criteria in the SLL patients and aggressive lymphoma patients will be based on the International Working Group consensus response evaluation criteria in lymphoma (RECIL 2017).

Initial evaluation of the efficacy endpoints related to response will incorporate the data from the first 9 cycles of treatment. Any patient who receives at least one dose of study therapy is evaluable for response. Patients who have stable disease or a response by 9 cycles and continue treatment after 9 cycles will have response assessments including CT scans of the chest, abdomen, and pelvis (and neck if involved), preferably least every 12 weeks, or as clinically indicated until disease progression. Patients who do not have a response by 9 cycles but who have stable disease are eligible to stay on study treatment for up to a total of 24 cycles, with continue to have stable disease after 24 cycles or have a response after 9 cycles therapy, drug therapy can continue until disease progression.

Secondary efficacy endpoints in all cohorts include overall response rate (ORR), duration of response (DoR), disease control rate (DCR), PFS, and OS. For patients achieving a response, the response duration will be measured from the time at which criteria for CR, PR, or PR with lymphocytosis is first assessed until the date at which recurrent or progressive disease or death due to disease is documented. Stable disease, a component of DCR, is defined as at least 6 months from the start of MS-553 monotherapy until to first documentation of progressive disease (PD) in relapsed and refractory CLL/SLL patients. Progression free survival will be measured as the time from the first dose of the study drug until disease progression or death from any cause. Overall survival will be measured as the time from the study drug until death due to any cause. For the secondary efficacy endpoints of response duration, PFS, and OS, patients who have not progressed or died at the time of last known status will be censored at that time; for response duration and PFS, patients may also be censored at the time

of subsequent treatment if a prior progression is not documented. See Section 8, Statistics, for more complete details on censoring.

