2.5. Secondary Endpoints

Secondary endpoints in this study are related to clinical activity. These include the following:

[figure not shown]
- Objective response rate (ORR), with overall response defined as best response of complete response (CR), CR with incomplete marrow recovery (CRi), partial response (PR), or PR with lymphocytosis (PRwL) according to the 2008 International Workshop on Chronic Lymphocytic Leukemia Response Criteria (IWCLL) with modifications for treatment-related lymphocytosis.
- Duration of response (DoR), defined as time from first documentation of response to first documentation of progressive disease (PD) per 2008 IWCLL, first new therapy including allogeneic transplantation, or death due to any cause.
- Progression free survival (PFS), defined as time from first dose of study treatment to the first documentation of PD, first new therapy excluding allogeneic transplantation, or death due to any cause.
- Overall survival (OS), defined as time from first dose of study treatment to death due to any cause.
- Disease control rate (DCR) defined as the percentage of patients who have achieved CR, CRi, PR, PRwL and stable disease (SD). Duration of stable disease with stable disease defined as at least 6 months from the start of MS-553 monotherapy to first

documentation of progressive disease (PD) in relapsed and refractory CLL/SLL patients.

• Pharmacokinetics of MS-553 monotherapy, as well as the small molecule agents used in combination, acalabrutinib, or venetoclax.

[figure not shown]

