3.7. Response Assessment

Response data will be collected at screening and on day 1 of every cycle beginning with the first treatment visit and ending at the end of treatment visit, which should occur 30 (+ 7 days) after the last dose of study drug, if the condition of the patient permits, or up to the start of other anti-cancer therapy or investigational drug product(s), whichever is sooner. Patients who discontinue treatment for reasons other than progressive disease, use of other anticancer therapy or an investigational drug product, death, or withdrawal of consent will undergo response assessments every 12 weeks (± 7 days) until progressive disease occurs.

Response data consists of a combination of interviews, physical exams, labs, and scans. Not all labs and scans will be obtained at each time point. See Section 6.2 and Appendix 1 for complete details.

4. **PATIENT POPULATION**

CLL is most commonly a disease of the elderly, with a median age at diagnosis of 71, but disease has been witnessed in adults of all ages. This study is targeted at CLL adults of any age who meet the inclusion criteria for the cohort to which the patient is enrolled.

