8.8. Secondary Analyses: Efficacy

ORR will be calculated along with its 95% CI based on exact method. In the analysis of ORR, patients who do not have sufficient on-study tumor assessment to characterize response will be excluded from the denominator.

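### Sections 2.5 and 6.2.2 start duration of response by different rules: 6.2.2 leaves out CRi, which 2.5 counts as a response

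*Combined protocol and SAP*

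**What the plan says.** Section 2.5, repeated in the synopsis, defines the ORR responders as patients with a "best response of complete response (CR), CR with incomplete marrow recovery (CRi), partial response (PR), or PR with lymphocytosis (PRwL"). It then gives DoR as follows: "Duration of response (DoR), defined as time from first documentation of response to first documentation of progressive disease (PD) per 2008 IWCLL", with first new therapy and death from any cause also ending the response. CRi is one of the named responses, so a CRi starts the clock under this definition. The disease control rate in the same section again names CRi as its own category: "percentage of patients who have achieved CR, CRi, PR, PRwL and stable disease (SD").

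Section 6.2.2 restates the DoR rule. For responding patients, "the response duration will be measured from the time at which criteria for CR, PR, or PR with lymphocytosis is first assessed". CRi is not in that list. The section then sends the reader elsewhere, but only for censoring: "See Section 8, Statistics, for more complete details on censoring".

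In Section 8, the efficacy analysis in 8.8 deals with ORR alone: "ORR will be calculated along with its 95% CI based on exact method". It gives no start, event or censoring rule for DoR.

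**The concern.** The two sections are both current text and give two start rules for the same endpoint. A programmer could defend either one. Under 6.2.2 taken literally, the patients with a DoR are no longer the patients counted as responders in the ORR, and some durations are measured from a later date than the first documented response. In expansion cohorts of about 10 to 25 patients, a reader of the report would expect the number in the DoR table to equal the ORR numerator. Here it might not, and nothing in the plan would explain the gap.

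**Working it through.** The plan states no figure for DoR, so there is none to reproduce. The check compares the texts and then takes the possible delay from the assessment schedule.

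**1. The two rules side by side**

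| | Section 2.5 and synopsis | Section 6.2.2 |
|---|---|---|
| Response categories named | CR, CRi, PR, PRwL | CR, PR, PRwL |
| DoR start | First documented response, so any of the four | First time one of the three is met |
| Death as an end of response | Any cause | Attributed to the disease |
| New therapy without prior progression | Event | Censoring allowed |

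The first two rows are the point made here. The last two are further differences in the same passage.

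**2. What each rule gives, by order of response**

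- First response is CR, PR or PRwL: same start date under both rules, delay 0. A later CRi changes nothing.
- Only response is CRi: the start is the CRi date under 2.5. Under 6.2.2 there is none.
- CRi first, then a listed category: the start is the CRi date under 2.5 and the later date under 6.2.2.

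**3. Size of the delay in the third case**

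Delay = (number of 28-day cycles between the two assessments) × 28 days, ignoring visit windows.

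- Section 3.7: "Response data will be collected at screening and on day 1 of every cycle". One cycle: 1 × 28 = 28 days.
- CT schedule, A and B cohorts (Appendices 1A and 1B): after cycles 3, 6 and 9. (6 − 3) × 28 = 84 days; (9 − 6) × 28 = 84 days.
- CT schedule, C cohorts (Appendix 1C): after cycles 2, 6 and 9. (6 − 2) × 28 = 112 days; (9 − 6) × 28 = 84 days.
- After cycle 9, all cohorts: CT preferably every 12 weeks, 12 × 7 = 84 days.

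The minimum delay is therefore 28 days if the later category can be assigned from Day 1 data alone, and 84 to 112 days if it waits for the next scheduled CT. The response criteria are cited in Appendix 5 but not reproduced, so the documents do not show which applies.

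**4. What cannot be computed**

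With R responders in the ORR, of whom c have CRi only, the literal DoR set is R − c. A further f patients, with CRi first and a listed category later, have durations shortened by the delay above. The documents give neither c nor f. Late starts shorten individual durations, but dropping the CRi-only patients could move a median either way. So neither the size nor the direction of the effect on a cohort's DoR follows from the documents.

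**The case against.** The best reply is that the endpoint section already has the right rule. Section 2.5 covers CRi, whereas 6.2.2 sits under study procedures and may be only a restatement with a term dropped. Its sentence is addressed to patients who achieve a response, and a CRi-only patient is one by 2.5, so a duration is evidently meant to exist. CRi is itself a form of CR, so CR in 6.2.2 could be shorthand for both. Much of this stands: it makes an intention to exclude CRi unlikely. It does not remove the conflict. Section 2.5 lists CRi apart from CR in both the ORR and the disease control rate, 6.2.2 separates PR from PRwL in the same list, and no clause ranks one section above the other.

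A reader might infer that CRi responders will lose their DoR as a matter of plan. The documents do not support that, because it follows only if 6.2.2 is applied literally over 2.5.

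A reader might also infer a sizeable distortion of DoR, above all in Cohort C. Section 5.2.4.3 and Appendix 2C do anticipate neutropenia and other hematologic toxicity with venetoclax, but nothing links this to CRi as a first or only response. Any percentage loss or shortening would rest on invented patient records or an assumed responder count. Patients who pass through PR or PRwL first are untouched, and response data are collected every cycle.

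**Conclusion.** Wrong as written: an internal inconsistency in the start rule of a secondary endpoint, with a small expected impact. The consequences are conditional on 6.2.2 being applied as worded, and they reach only patients whose first response is CRi. ORR is not affected. Section 8.4 states that there is no formal hypothesis, so no test depends on DoR. The point is still worth correcting because a stated rule, followed exactly, gives a result that contradicts the endpoint definition, and the efficacy text in Section 8 does not resolve it.

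**What to change.** Minimum change: add CRi to the list of responses in Section 6.2.2, so that DoR is computed in exactly the ORR responders.

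Preferred change: replace the DoR sentence in 6.2.2 with a statement that DoR is as defined in Section 2.5. This settles the start date and also removes the difference on deaths. For the difference on new therapy to go as well, the reference has to govern the later sentence in 6.2.2 that allows censoring at subsequent treatment, so response duration should be taken out of that clause.

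Either change is a few words of protocol text. Neither alters data collection, visits or sample size.
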